4.1 Planned Covariates

The following baseline characteristics are specified as potential confounding covariates:

- Stratification factor of tumor type (Gastrointestinal, **Pancreatic**, Colorectal) Stratification factor of baseline platelet count ($< 50 \times 10^9/L$, $\geq 50 \times 10^9/L$)
- Age (continuous and categorized ≤ 65 years, > 65 years)
- Sex (Male, Female)
- Race (White, Black or African American, Asian, American Indian or Alaska Native, Other)
- Ethnicity (Hispanic or Latino, Not Hispanic or Latino)
- Region (United States, Europe, Rest of World)
- Body mass index
- ECOG (0–1, ≥ 2)
- Stage of disease (Stage 1 to 3, Stage 4 or recurrent disease)
- Line of chemotherapy treatment (1, ≥ 2)
- **Type of chemotherapy regimen (FOLFOX, FOLFIRINOX, FOLFOXIRI, CAPEOX)**
- Number of previous chemotherapy cycles (≤ 2 , > 2)
- Prior or Concurrent Bevacizumab use (Yes, No)
- Baseline platelet count (continuous)
- Prior bleeding events (Yes, No)

- Prior platelet transfusions (Yes, No)
- Prior use of erythropoiesis-stimulating agent (Yes, No)
- Prior use of granulocyte colony-stimulating factor (Yes, No)
- Prior use of programmed cell death 1 inhibitors or programmed cell death ligand 1 inhibitors (Yes, No)
- Concurrent use of programmed cell death 1 inhibitors or programmed cell death ligand 1 inhibitors (Yes, No)

4.2 Subgroups

The study is not powered to draw conclusions from subgroup analyses. However, exploratory analyses will be conducted to examine the consistency of the treatment effect on the primary and key secondary endpoints. Subgroup analyses will be performed for the following covariates when each subgroup has at least 10% of the subjects in the analysis set:

- Sex (Male vs Female)
- Stage of disease (Stage 1 to 3, Stage 4 or recurrent disease)
- Prior or Concurrent Bevacizumab use (Yes, No)
- Number of previous chemotherapy cycles (≤ 2 , > 2)
- **Type of chemotherapy regimen (FOLFOX, FOLFIRINOX, FOLFOXIRI, CAPEOX)**
- Baseline platelet count ($< 50 \times 10^9/L$, $\geq 50 \times 10^9/L$) (stratification factor)
- Tumor type (Gastrointestinal, **Pancreatic**, Colorectal) (stratification factor)

5. Definitions

Baseline

Baseline is defined as the value measured on the randomization date, i.e., study day 1. If measurement was not available on randomization date, the latest measurement before randomization date may be used.

Chemotherapy Cycle Status

Chemotherapy cycle status is information on whether a given on-study chemotherapy cycle was administered as planned or was modified, and the reason for modification. Chemotherapy modifications include dose reduction, dose delay, dose omission and treatment discontinuation.

Concurrent Use of Medication at Baseline

Concurrent use of medication at baseline means the medication has been administered on or after the start of the current chemotherapy regimen.

This derivation will be used to derive efficacy covariates variables of prior or concurrent bevacizumab use (Yes, No), prior use of erythropoiesis-stimulating agent (Yes, No), prior use of granulocyte colony-stimulating factor (Yes, No), prior use of programmed cell death 1 inhibitors or programmed cell death ligand 1 inhibitors (Yes, No), concurrent use of programmed cell death 1 inhibitors or programmed cell death ligand 1 inhibitors (Yes, No).

Duration-Adjusted Event Rate for Adverse Events (AE) during the Treatment Period

The duration-adjusted AE incidence rate within a treatment group is expressed as the number of events per 100 subject-years from the study day 1 until the date of last dose of investigational product plus 30 days or EOS, whichever is earlier:

$$\text{Duration-adjusted event rate} = \frac{\text{Total number of events}}{\text{Total duration in subject-years}} \times 100$$

Duration-Adjusted Event Rate for AE during the Follow-up Period

The duration-adjusted AE incidence rate within a treatment group is expressed as the number of events per 100 subject-years from the 31 days after the date of last dose of investigational product to EOS:

$$\text{Duration-adjusted event rate} = \frac{\text{Total number of events}}{\text{Total duration in subject-years}} \times 100$$

Endpoints: Primary - No Thrombocytopenia-induced Modification of any Myelosuppressive Treatment Agent in the Second and Third Cycles

Subjects will meet the criteria of the primary endpoint if there is no thrombocytopenia-induced modification of any myelosuppressive treatment agent in the second and third cycles of the planned on-study chemotherapy regimen.

A thrombocytopenia-induced modification is defined as any dose reduction, dose delay, dose omission, and/or early chemotherapy treatment discontinuation due to low platelet counts less than $100 \times 10^9/\text{L}$.

For the purposes of determining dose reductions, the actual on-study chemotherapy doses will be compared to the planned chemotherapy dose recorded on study day 1, defined by the dose administered in the chemotherapy cycle immediately prior to study entry.

For the purposes of determining dose delays, the difference between the start date of a given chemotherapy cycle and the start date of the chemotherapy cycle immediately prior to the given cycle will be calculated and compared to the planned cycle length of the regimen.

Delayed, reduced, omitted, and discontinued doses within a cycle will also be counted as dose modifications even if they do not cause the start of the next cycle to be delayed. Note: For subjects who discontinue investigational product prior to completing 3 cycles of chemotherapy, chemotherapy dose and schedule should be recorded through 3 on-study chemotherapy cycles to the end of the third on-study cycle.

An independent adjudicator will periodically verify the reason for chemotherapy dose reduction, dose delay, dose omission and treatment discontinuation during on-study cycles 1-3. For each planned chemotherapy agent, any dose delays, dose reduction, dose omission, and treatment discontinuation at any time during on-study cycle 2 or 3, where the adjudicated reason is thrombocytopenia, will be counted as failure in the primary endpoint analysis. Chemotherapy dose modification in the first cycle of the planned on study chemotherapy regimen will not be counted toward the primary endpoint even if due to CIT. If a chemotherapy dose modification occurs during on-study cycle 1 the new baseline for comparison will reset to the chemotherapy dose modifications that occurred in cycle 1. This will also apply to dose modifications occurring during on study cycle 2 that are not attributable to CIT.

Chemotherapy dose delays dose reductions, and dose omissions will be permitted according to chemotherapy dose modification outline in section 7.4.1.2 of the protocol.

Endpoints: Secondary (1) – Platelet Count Nadir from the Start of the First On-study Chemotherapy Cycle through the End of the Treatment Period

The platelet count nadir from the start of the first on-study chemotherapy cycle through the EOTP is defined as the lowest platelet count observed after the date of the earliest myelosuppressive chemotherapy agent delivered in the first on-study cycle through the EOTP day.

For subjects who never started the first on-study chemotherapy cycles or who never have platelet count measured after the first on-study chemotherapy cycle, the platelet count at baseline will be used for the endpoint.

Endpoints: Secondary (2) – Time to First Platelet Response

Time to first platelet response is defined as the number of days from study day 1 to the date of achieving a platelet count $\geq 100 \times 10^9/L$ **in the absence of platelet transfusions during the preceding 7 days**. It is calculated as:

Date of first platelet response – study day 1 + 1.

If a platelet transfusion occurred during the 7 days preceding a platelet count then that platelet count will not be considered a response event if it is $\geq 100 \times 10^9/L$. Subjects who did not achieve a response event during the treatment period are censored at their last platelet count assessment date up to EOTP or at **randomization date** if they did not have any **post-baseline** platelet assessments.

Endpoints: Secondary (3) – Duration-adjusted Event Rate of \geq Grade 2 Bleeding Events

The duration-adjusted event rate (**events/100 subject-years**) is defined as the number of grade ≥ 2 bleeding events, divided by the total duration (in 100 subject-years) that subjects have been on study from study day 1 to the earliest of last dose of IP + 30 days or EOS.

Bleeding events will be recorded on the adverse events case report form (CRF) and graded using the CTCAE version 5.0. Bleeding events will be identified using the narrow search of haemorrhages standardized MedDRA query (SMQ), using the MedDRA version 25.1 or later.

Abbreviations:

- b.events = Bleeding Events (Haemorrhages)
- Status = 1 (recurrence of b.event)
- Status = 0 (no b.event)

Censoring Rules:

- Subject with at least one or more than one “grade ≥ 2 b.events”
 - Subject may report multiple b.events, each b.event will be flagged with “Status = 1”.
 - Subject may report multiple b.events, if any b.event end date is missing then also “Status = 1”.
 - The treatment period from last b.event start date to Min(last dose of IP date+30, Study End date) will be considered as no event period, reported as “Status = 0”
- The subjects who do not report any “grade ≥ 2 b.events”
 - These subjects will be included in analysis with “Status = 0”.

Notes:

Status variable will be assigned considering “Haemorrhages” SMQ only, irrespective of number of other adverse event(s) experienced by subject.

- **Status is the censoring variable which will be utilized into the PHREG.**

Endpoints: Secondary (4) –Overall Survival

Overall survival time will be calculated from study day 1 to death. Subjects who have not died will be censored at their last date of contact.

Endpoints: Secondary (5) – Platelet Transfusion

Platelet transfusions during the treatment period is defined as a subject having at least one platelet transfusion after during study period as recorded on the transfusions CRF.

Endpoints: Secondary (6) – Achieving a platelet count $\geq 100 \times 10^9/L$

Achieving a platelet count $\geq 100 \times 10^9/L$ at any time after study day 1, up to and including the date of the week 4 visit (ie, 7 days after the third planned dose of investigational product). if a platelet transfusion occurred during the 7 days preceding a platelet count, then that platelet count will not be considered as achieving the endpoint even if it is $\geq 100 \times 10^9/L$. Subjects who have no platelet counts during this period will be considered as not achieving achieved a platelet count $\geq 100 \times 10^9/L$. For subjects who never received IP, the subjects are considered as not achieving a platelet count $\geq 100 \times 10^9/L$. Weeks with no platelet count measurements (missing data) are considered as not achieving a platelet count $\geq 100 \times 10^9/L$.

Endpoints: Secondary (safety) – Myelodysplastic Syndromes (MDS) Free Time

Myelodysplastic syndromes (MDS) free time is defined as the time from the first dose of IP to the first occurrence of MDS. Subjects who have not had an MDS event will be censored at their last contact date or death date, whichever is later.

It is calculated as:

Date of first occurrence of MDS or censoring date – the date of the first dose of IP + 1.

MDS events will be identified using the narrow search of myelodysplastic syndromes (SMQ), using the MedDRA version **25.1** or later available at the time of the analysis.

Endpoints: Secondary (safety) – Myelodysplastic Syndromes (MDS) Free Survival Time

MDS free survival time is defined as the time from the first dose of IP to the first occurrence of MDS or death, whichever is earlier. Subjects who have not had an MDS event and have not died will be censored at their last contact date. It is calculated as:

Date of first occurrence of MDS, death or censoring – the date of the first dose date of IP + 1.

MDS events will be identified using the narrow search of myelodysplastic syndromes (SMQ), using the MedDRA version **25.1** or later available at the time of the analysis.

Endpoints: Secondary (safety) – Secondary Malignancy Free Time

[figure not shown]
Secondary malignancy free time is defined as the time from the first dose of IP to the onset of a secondary malignancy. Subjects without an event will be censored at their last contact date or death, whichever is later. It is calculated as:

Date of onset of secondary malignancy or censoring – the date of the first dose IP + 1.

Endpoints: Secondary (safety) – Secondary Malignancy Free Survival Time

Secondary malignancy free survival time is defined as the time from the first dose of IP to the onset of a secondary malignancy or death, whichever is earlier. Subjects without an event will be censored at their last contact date. It is calculated as:

Date of onset of secondary malignancy, death or censoring – the date of the first dose date of IP + 1.

Last Contact Date

The latest date on which a subject is known to alive.

Myelosuppressive Treatment Agents

Myelosuppressive treatment agents are those agents in the on-study chemotherapy regimen that are 5-fluorouracil **or capecitabine and oxaliplatin (plus irinotecan in FOLFIRINOX or FOLFOXIRI) (Oxaliplatin)-based chemotherapy regimen.**

On-study Chemotherapy Regimens

The on-study chemotherapy regimen is the chemotherapy regimen planned to be taken after study day 1. It will be the same chemotherapy regimen taken in the last chemotherapy cycle immediately before study day 1.

Platelet Counts

If there are multiple platelet values performed on a study visit date, the platelet value most immediately prior to **non-IP** administration **will be selected**, as the platelet value for that study visit date. **If no platelet value prior to non-IP administration, the platelet value prior to IP administration will be selected.**

Prior Use of Medication at Baseline

Prior use of medication at baseline means the medication has been administered prior to the start of the current chemotherapy regimen.

Randomization Date

Randomization date is defined as the date the subject is randomized to a treatment group. Per protocol, subjects should initiate IP the same day they are randomized.

Study Day 1

Study day 1 is defined as the randomization date. **If the randomization date and the first IP administration date are the same, then study day 1 is the randomization date for both efficacy and safety analysis.**

If randomization date and subject first IP administration date are different then study day 1 will be derived using first IP administration date.

Study Day

For dates occurring on or after the study day 1 date, study day will be calculated as:

Date of interest - **date of first IP administration** + 1.

For dates occurring before the study day 1 date, study day will be calculated as:

Date of interest - **date of first IP administration.**

Treatment-emergent Adverse Event

Events categorized as AEs starting on or after first dose of investigational product as determined by “Did event start before first dose of investigational product” equal to “No” or missing on the Events eCRF; and up to and including 30 days after the last dose of investigational product (excluding events reported after End of Study date).

Any event which has started 30 days after the last dose of IP (i.e., during LTFU period) will not be considered as TEAE.

[figure not shown]
6. Analysis Sets

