### Diagnostic Assessments

218 Anemia (hemoglobin < 80 g/L [8 g/dL]) on the day of initiation of investigational product as assessed by local labs. Use of red cell transfusions and erythropoietic stimulating agents is permitted throughout the study as per institutional guidelines.

219 Neutropenia (absolute neutrophil count < 1 x 10^9/L) on the day of initiation of investigational product as assessed by local labs. Use of granulocyte-colony stimulating factor is permitted throughout the study as per institutional guidelines.

232 Abnormal renal function with creatinine clearance < 30 mL/min using the Cockcroft-Gault estimated creatinine clearance as assessed by **local** laboratory during screening. **If local laboratory results are not available, use central laboratory results.**

233 Abnormal liver function (total bilirubin > 3 X ULN; alanine aminotransferase [ALT] or aspartate aminotransferase [AST] > 3 X ULN for subjects without liver metastases or ≥ 5 X ULN for subjects with liver metastases) as assessed by **local** laboratory during screening. **If local laboratory results are not available, use central laboratory results.**

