### 10.2.2 Covariates

The following baseline characteristics are specified as potential confounding covariates:

- Stratification factor of tumor type (Gastrointestinal, Pancreatic, Colorectal)
- Stratification factor of baseline platelet count ( $< 50 \times 10^9/L$ ,  $\geq 50 \times 10^9/L$ )
- Age (continuous and categorized  $\leq 65$  years,  $> 65$  years)
- Sex (Male, Female)
- Race (White, Black or African American, Asian, American Indian or Alaska Native, Other)
- Ethnicity (Hispanic or Latino, Not Hispanic or Latino)
- Region (United States, Europe, Rest of World)
- Body mass index
- ECOG (0–1,  $\geq 2$ )
- Stage of disease (Stage 1 to 3, Stage 4 or recurrent disease)
- Line of chemotherapy treatment (1,  $\geq 2$ )
- Type of chemotherapy regimen (FOLFOX, FOLFIRINOX, FOLFOXIRI, CAPEOX)
- Number of previous chemotherapy cycles ( $\leq 2$ ,  $> 2$ )

- Prior or Concurrent Bevacizumab use (Yes, No)
- Baseline platelet count (continuous)
- Prior bleeding events (Yes, No)
- Prior platelet transfusions (Yes, No)
- Prior use of erythropoiesis-stimulating agent (Yes, No)
- Prior use of granulocyte colony-stimulating factor (Yes, No)
- Prior use of programmed cell death 1 inhibitors or programmed cell death ligand 1 inhibitors (Yes, No)
- Concurrent use of programmed cell death 1 inhibitors or programmed cell death ligand 1 inhibitors (Yes, No)

Concurrent use of medication at baseline means the medication has been administered on or after the start of the current chemotherapy regimen.

Descriptive analyses will be provided including summary statistics for continuous covariates and percentage of subjects by each level of categorical covariates.

For each above specified covariate, sensitivity analyses will be explored to evaluate any potential confounding: (1) a 2-sided CMH test checking conditional independence between treatment groups and primary endpoint outcomes controlling for each individual covariate, (2) a logistic regression with primary endpoint outcome as dependent variable and explanatory variables from treatment group, the specified covariate, interaction of treatment by covariate.

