9.5.1 Analyses of Primary Efficacy Endpoint(s)

The primary endpoint is the proportion of subjects with no thrombocytopenia induced dose modification. **The primary analysis will be based on the adjudication committee (AC) assessment of thrombocytopenia-induced dose modification. The proportion along with a 95% CI will be provided for each treatment group.** A 2-sided CMH test will be used to compare groups controlling for the stratification factors of tumor type and baseline platelet count. The Mantel-Haenszel estimate of common odds ratio for romiplostim vs placebo will be estimated along with a 95% CI for each treatment group and the difference in proportions between treatment groups will be provided with a 95% CI.

For primary analysis, subjects with missing observations for cycle 2 and/or cycle 3, or who discontinued any myelosuppressive agent early, are considered as not meeting the criteria of the primary endpoint. The following sensitivity analyses will be explored:

A sensitivity analysis using the investigator's assessment on thrombocytopenia -induced dose modification will be performed. The number and percentage of subjects with concordant and discordant assessments per investigator and AC will be summarized.

If more than 10% of subjects in the full analysis set have COVID-19 related IPDs with missing chemotherapy without platelet count assessment for cycle 2 or cycle 3, a sensitivity analyses may be explored by excluding those subjects with COVID-19 related IPDs.

For each specified covariate in [Section 4.1](#), sensitivity analyses will be conducted to evaluate any potential confounding: (1) a 2-sided CMH test checking conditional independence between treatment groups and primary endpoint outcomes controlling for each individual covariate, (2) a logistic regression with primary endpoint outcome as the dependent variable and explanatory variables from treatment group, the specified covariate, and interaction of treatment by covariate.

Subgroup exploratory analyses will also be performed to explore the consistency of the treatment effect between subgroups described in [Section 4.2](#). FAS will be used for the primary endpoint analysis.

9.5.2 Analyses of Secondary Efficacy Endpoint(s)**9.5.2.1 Depth of Platelet Count Nadir From the Start of the First On-study Chemotherapy Cycle Through the EOTP (1)**

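### SAP section 5 assigns the concurrent-use derivation to three prior-use covariates and to prior-or-concurrent bevacizumab, contradicting its own definition of prior use and stating no end date

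*SAP*

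**What the plan says.** SAP section 4.1 lists, among others, prior or concurrent bevacizumab, prior ESA, prior G-CSF, prior PD-1/PD-L1 inhibitor and concurrent PD-1/PD-L1 inhibitor use, under the sentence "The following baseline characteristics are specified as potential confounding covariates".

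SAP section 5 holds two definitions that bear on them.

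- The entry on concurrent use repeats Protocol section 10.2.2: "Concurrent use of medication at baseline means the medication has been administered on or after the start of the current chemotherapy regimen". The SAP then adds a sentence that the protocol does not have: "This derivation will be used to derive efficacy covariates variables of prior or concurrent bevacizumab use (Yes, No), prior use of erythropoiesis-stimulating agent". It goes on to name the other three covariates.
- Later in the section comes the entry on prior use: "Prior use of medication at baseline means the medication has been administered prior to the start of the current chemotherapy regimen". No covariate is tied to it.

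The covariates are used in three places. SAP section 9.5.1 plans, for each one, "a 2-sided CMH test checking conditional independence between treatment groups and primary endpoint outcomes controlling for each individual covariate" and a logistic regression with a treatment-by-covariate interaction. SAP section 4.2 makes bevacizumab use a subgroup for the primary and key secondary endpoints. SAP section 9.4 tabulates all five at baseline. SAP section 10 states that nothing departs from the protocol-specified analyses.

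**The concern.** The only sentence that tells a programmer how to derive the prior-use covariates points to the definition of concurrent use, which covers the complementary period. A check for confounding by earlier treatment would then be run on a variable that does not measure earlier treatment, and the baseline table would label current-regimen use as prior use.

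A second gap is that the derivation gives a start but no end. Protocol section 6.2 allows both supportive drug classes after randomisation: "Use of granulocyte-colony stimulating factor is permitted throughout the study as per institutional guidelines" and "Use of red cell transfusions and erythropoietic stimulating agents is permitted throughout the study as per institutional guidelines". Protocol section 7.8.2 collects concomitant therapies until both safety follow-up visits are complete, so such records can be in the data. Use after randomisation may depend on the assigned arm and on how much chemotherapy was delivered, and chemotherapy delivery is the primary outcome. Adjusting for it could introduce bias into an analysis meant to look for confounding.

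**Working it through.** No figure in the plan is in question, so the check applies the two definitions to each possible timing of drug use.

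**Step 1. A prior-use covariate (ESA, G-CSF or PD-1/PD-L1), for a subject already on the current regimen at day 1.**

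| Timing of use | Prior-use definition (SAP 5) | Assigned rule, day 1 cut-off inferred | Assigned rule, no cut-off |
|---|---|---|---|
| Never | No | No | No |
| Only before the current regimen | Yes | No | No |
| First during the current regimen, before day 1 | No | Yes | Yes |
| Before the current regimen, and during it before day 1 | Yes | Yes | Yes |
| Before the current regimen, then again only after day 1 | Yes | No | Yes |
| Only after day 1 | No | No | Yes |

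Row 2 is wrong in the negative direction and row 3 in the positive direction, whether or not a cut-off is inferred. The missing end date matters only in the last two rows. The main defect therefore does not depend on how the end-date question is resolved.

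**Step 2. PD-1/PD-L1 inhibitors.** The same rule is assigned to the prior and the concurrent variable, so the two take the same value in every subject. SAP sections 4.1 and 9.4 list them as separate covariates.

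**Step 3. Bevacizumab.** The name of the covariate calls for Yes if either definition is met. Under the assigned rule, use only before the current regimen gives No, so the prior half of the variable is lost.

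**Step 4. Count.** Five covariates are named in the sentence. Concurrent PD-1/PD-L1 is correctly assigned. The other four (prior ESA, prior G-CSF, prior PD-1/PD-L1, and prior or concurrent bevacizumab) are not.

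**Step 5. Meaning of the current regimen.** The second option of inclusion criterion 109 (Protocol section 6.1) admits subjects who have thrombocytopenia from a non-protocol regimen and are only planning a protocol regimen. Protocol section 7.4.1.2 bars the first on-study cycle before study week 2. If the current regimen is taken to be the planned one, it starts after day 1, and a concurrent window that closes at day 1 is empty. If it is the last pre-study regimen, both definitions work. SAP section 5 describes the on-study regimen as the one taken in the cycle just before day 1, which does not fit these subjects. The documents do not settle the point.

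**Step 6. Data capture.** Protocol section 7.8.1 collects prior anti-cancer therapies from 3 years before enrolment, with start and stop dates, which should cover bevacizumab and PD-1/PD-L1 inhibitors within that period. For other prior therapies it gives radiotherapy as its example. Section 7.8.2 covers concomitant therapies. Neither clearly says that G-CSF or ESA use that ended before the current regimen is recorded.

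**The case against.** The best answer is that this is a misplaced sentence and not a chosen analysis. The prior-use definition sits in the same section in matching form, the list mixes prior and concurrent variables, and a reading that merges two listed covariates cannot have been intended. The protocol never applies the concurrent definition to the prior-use variables. A careful programmer might infer the right rule. All of that is fair and makes the fix easy, but it leaves a written derivation that gives wrong values if followed.

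On timing, a reader might infer that the planned analyses do condition on drugs given after randomisation. The documents do not support that. The defined term is use at baseline, the covariates are called baseline characteristics, and SAP section 5 states "Baseline is defined as the value measured on the randomization date, i.e., study day 1". Together these favour a day 1 cut-off. What stands is that the derivation does not state one, and the baseline entry is worded for measurements, not for medication intervals. Permission to use G-CSF or ESAs on study shows that post-randomisation use could be counted, not that it will be.

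Two other inferences also go too far. One is that for subjects entering by the second option of criterion 109 only post-randomisation use can count; that depends on one reading of an undefined term. The other is that the adjusted odds ratio would shift by a particular amount; the documents give no rates of use of these drugs and no relation to arm or outcome.

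Finally, the reach is small. These are one-at-a-time sensitivity analyses, a subgroup the study is not powered for, and a descriptive table. That is correct.

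**Conclusion.** The derivation in SAP section 5 is wrong as written for four of the five covariates it names. It contradicts the SAP's own definition of prior use, miscodes subjects treated only before the current regimen and those first treated during it, and makes prior and concurrent PD-1/PD-L1 use one variable. These results need no assumption beyond following the sentence literally. The missing end date is a weaker, secondary point: a gap that invites a programming error, with the surrounding text leaning toward day 1.

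The effect is confined to the single-covariate CMH and logistic sensitivity analyses of the primary endpoint, the bevacizumab subgroup and the baseline table. The primary CMH test adjusts only for the two stratification factors, so it is unaffected, as are power and the testing hierarchy. No magnitude can be derived from the documents. The correction is worth making because a stated rule yields wrong values and is simple to repair.

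**What to change.** Amend SAP section 5 as follows.

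1. Derive prior ESA, prior G-CSF and prior PD-1/PD-L1 use from the existing definition of prior use.
2. Keep the concurrent-use definition, on its own, for concurrent PD-1/PD-L1 only.
3. Code bevacizumab Yes if either definition is met.
4. Close the concurrent window before the first dose of investigational product.
5. State which regimen is current for subjects entering by the second option of criterion 109, for example the last pre-study regimen.
6. Confirm that G-CSF and ESA use before the current regimen is captured with dates. If it is not, say so and limit or drop those two covariates.

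Items 1 to 5 take a few sentences and a matching change to the derivation specification, with no effect on the primary analysis. Item 6 is a check of the case report form; its cost depends on the answer, which the documents do not give.
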